# 7.5. **Emergency Unblinding**

In this trial, the treating clinicians and participants are already unblinded to intervention, so it is not expected that there will be any need to unblind any blinded team members to ensure emergency care.

#### 7.6. Baseline Assessments and Data

Baseline data for PWD and their informal carers consenting to the study will be collected by a clinical researcher within two weeks of confirmation of eligibility. For PWD, this will include the DAD, EQ-5D-5L, QOL-AD, Short-FES-I and Timed Up and Go test. GAS will be collected by the intervention therapist at baseline for those randomised to the intervention (Table 2). Informal carers will be asked to complete EQ-5D-5L proxy, QOL-AD proxy, HUQ, EQ-5D-5L and ZBI (Table 2).

After the baseline assessment, the clinical researcher will inform the central research team. If the participant is in the intervention arm, the referral will be sent to the intervention team using a structured referral form with details of the baseline assessment of the PWD and the unpaid carer. The intervention team will then arrange an initial intervention assessment within two weeks. If the participant is in the control arm, usual care will continue.

#### 7.7. Follow up Assessments

The clinical researcher will carry out a second visit to repeat most of the outcome measures completed at baseline with the PWD and their informal carer (see Table 2). For those in the intervention arm, this will take place 26 weeks after the start of the intervention. For those in the control arm, this will take place 28 weeks from baseline. The HUQ will also be completed at three months follow up by phone call. A fidelity checklist will be used to measure intervention fidelity.

#### 7.8. Quantitative assessment of falls

PWD will be asked to complete a prospective falls diary for the duration of the six month follow up period with the aid of an unpaid carer if required. These will be used to calculate:

Page 36 of 59

- the fall rate per person per year
- the proportion of participants with one or more falls
- injury and fracture rates

### 7.9. Process evaluation and Qualitative assessment of study procedures

The process evaluation will examine implementation and the acceptability of the intervention for participants and professionals, and mechanisms of impact, including the roles of geriatricians and carer support identified in the previous study as being important. The process evaluation will be structured using a logic model, representing an initial theory of how the intervention works. Eighteen semi-structured, face-to-face interviews will be conducted with PWD receiving the intervention and their unpaid carers (paired interviews) to identify factors affecting acceptability and mechanisms of impact. Patient-carer pairs will be sampled for maximum variation, and interviews will be conducted around the end of the intervention to avoid Hawthorne effects.

Twenty-four semi-structured telephone interviews with professionals will be conducted to examine implementation, implementability (including fidelity, and mechanisms of impact, behaviour change, contextual factors). Interviews will be conducted across the 3 intervention sites and with four types of professional: geriatricians, physiotherapists, occupational therapists and support workers. During the trial delivery phase, six observations of professionals will be conducted to further investigate implementation and contextual factors. Four supervision and four multidisciplinary team meetings will also be observed. Field notes will include a reflexive perspective.

Interviews will also include questions about the acceptability and feasibility of study procedures, such as recruitment and randomisation, where professionals have been involved in these aspects of the study.

The consent process with PWD and unpaid carers will also include consent for optional participation in the qualitative aspects of the study. Interviews will take no longer than around 60 minutes and will be audio recorded with participants' permission (as documented on the initial study consent form; consent to recording will be verbally confirmed at the time of the interview).

Page 37 of 59

Maintain Study Protocol IRAS ID: 323555 Version: 3.0 Date: 08/11/2023

Table 3 Schedule of Events

	Baseline assessment (clinical researcher)	Week 1 (intervention)	Weeks 2-28 (intervention)	Week 12 follow- up assessment (clinical researcher)	Week 28 follow- up assessment (clinical researcher)
Informed consent (including consent for observation and/or interview)	X				
Baseline data collected (see Table 2)	Х				
2 Assessment visits by Intervention team including Timed Up and Go Test		X			
Up to 22 visits by Intervention team			X		
Final visits will include Goal attainment scaling and Timed Up and Go test					
Completion of diary		X	X		
Completion of HUQ	X			X	X
Informed consent of professionals and participants and observation of interventions received		X	X		
Informed consent and qualitative interview with some professionals regarding views on intervention.			X		
Qualitative interview with patients, informal carers and professionals views on intervention (subset of participants who consent to qualitative study)			X		
Follow up outcome data collected					Х

#### 7.10. Withdrawal Criteria

Both PWD and their unpaid carers have the right to withdraw from any and all aspects of the study without giving a reason at any time. Investigator sites should attempt to determine the reason for withdrawal and document this within the CRF and participant's medical notes. PWD and their unpaid carers will be able to withdraw from the optional qualitative component, intervention delivery and/or outcome assessment. It is the responsibility of the site to communicate with the participant to determine which aspect of the study they wish to withdraw from. This information will be documented on a study withdrawal form.

The investigator may withdraw a participant form the study at any time if they consider it necessary for any reason, including:

- Participant withdrawal of consent
- Significant protocol deviation or non-compliance
- Investigator's discretion that is in the best interest of the participant
- An adverse event (AE) that causes the participant to be unable to continue in the study
- Termination of the study by the sponsor

Due to the nature of dementia, some participants may become ill or die before completion of the study. Routinely, participants who withdraw will not be replaced in the trial.

Professionals will have to the right to withdraw from the study at any time without having to give a reason.

# 7.11. End of Study

The end of the study will be defined as the completion of all data collection, all data recorded in the study database, all data cleaned, and the database locked. A declaration of end of study form will be submitted to the NHS REC who awarded the favourable opinion within 90 days of the end of study.

If the study is terminated early, the end date will be the date that the Sponsor formally declare the study terminated in writing. The NHS REC will be notified of early termination within 15 days of the Sponsor deciding to end the study.

#### 8. Maintain Intervention

### 8.1. Description of the Intervention

The Maintain intervention is a multidisciplinary complex intervention which is delivered in the patient participant's home. The intervention will be personalised to each participant, taking into account their physical abilities, their preference for activities and goals agreed by the therapist, the patient participant and their unpaid carer. The number of sessions the participant receives will also be tailored to their needs. The first two sessions will be assessment sessions which will be followed by up to 19 therapy sessions delivered over 12 weeks and booster sessions at 16 weeks, 20 weeks and 24 weeks. An intervention manual will detail the assessment and therapy procedures for the professionals.

### 8.1.1. Training

Use of the manual will be accompanied by training sessions for professionals responsible for the delivery of the intervention prior to enrolment of the first participant. Training will be offered online as e-learning modules and/or face-to-face. The physiotherapist and occupational therapist with expertise in working with PWD will deliver the training. Training will include:

- Dementia awareness
- Dementia identification, assessment and diagnosis
- Dementia risk reduction and prevention
- Person-centred dementia care
- · Communication, interaction and behaviour in dementia care
- Health and well-being in dementia care
- Assessment and management of pain
- Pharmacological interventions in dementia care
- Living well with dementia and promoting independence
- · Families and carers as partners in dementia care
- Equality, diversity and inclusion in dementia care
- Law, ethics and safeguarding in dementia care
- End of life dementia care
- Research and evidence-based practice in dementia care
- Setting SMART goals
- Goal Attainment Scaling (GAS)

#### 8.1.2. Assessment sessions

The PT and/or OT will visit the participant during week 1 to complete a structured holistic assessment proforma assessing the below items. This assessment will include perspectives of the participant and their unpaid carer as well as discussion with professionals already involved with the participant.

- History and circumstances of index fall(s) and any injuries sustained
- History of additional falls to determine any patterns in falling
- Details of treatment offered so far and services already involved
- Past medical history and comorbidities
- Medication
- Osteoporosis risk

Page 40 of 59

- Living arrangements
- Details of current informal and formal carer input
- · Current levels of activity, routines and likes and dislikes for activities
- Current mobility (bed mobility, bed and chair transfers, walking and stairs)
- Assessment of risk factors for falls
  - Fear of falling
  - Dizziness
  - Nutrition and fluid intake
  - o Pain
  - Continence
  - Footwear
- Identification of challenging behaviours and sleep disturbance
- Identification of informal carer stress
- Identification of informal carer's willingness to be involved in promoting the activities
- Physical examination
  - Objective body examination including focus on areas of pain
  - o Timed Up and Go test
  - o Use of walking aids
  - o Functional movements e.g. reaching, carrying and bending
  - Lying and standing blood pressure
  - Visual assessment
- Functional examination
  - Assessment of home safety environment including a walk around the home to see where actual falls have occurred
  - o Assessment of functional activities e.g. ability to make a cup of tea
  - Assessment of home adaptations and need for new adaptations

A problem list and set of goals to achieve will be compiled at the end of the assessment which will be agreed with both the participant and their unpaid carer. The goals and problem list will then be discussed at a multidisciplinary team (MDT) meeting with the physiotherapist, OT and support worker. The MDT will create an action plan including recommendations for activities to be carried out during the therapy sessions. One therapist will be identified as the participant's key worker. At week 6, the goals and action plan will be reviewed and adjusted by the key worker if required.

Onward referrals to the GP, geriatrician, mental health nurse, old age psychiatrist, continence adviser, podiatrist, optician or dietitian will also be identified by the MDT.

The initial assessment session will also confirm the unpaid carer's capacity and willingness to take part in the intervention, their knowledge and understanding of dementia and falls (including attitudes to risk) and an assessment of carer stress (using data from the ZBI as a guide). The MDT will also consider the needs of the unpaid carer and how to address these needs. An action plan for the unpaid carer's needs will be made where appropriate.

#### 8.1.3. Therapy sessions

Each therapy session will be 60 minutes with up to 19 sessions occurring over a 12 week period. Booster sessions will also take place at weeks 16, 20 and 24. In total the participant could receive a maximum of 22 sessions (including the boosters) over the course of the 6 month follow-up period. The number and frequency of the sessions will be tailored to the participants needs and if the participant is making good progress they may wish to have fewer than 19 sessions during the 12 week period. Up to 3 sessions will

Page 41 of 59

be delivered by the physiotherapist and up to 3 sessions will be delivered by the occupational therapist. All remaining sessions will be delivered by a rehabilitation support worker (RSW).

The participant's comfort, nutritional needs and pain assessment will be considered before each activity session with tools to assess non-verbal signs of pain used if appropriate. Activities include both functional activities and/or physical exercises (which may include strength and balance exercises and dual task activities). Participants can either follow an exercise programme separate from their daily activities or have the exercises embedded into their daily life e.g. practicing balancing whilst standing at the sink washing up. Functional activities will be identified during the goal setting session and will include encouragement to engage in both community and social activities. Unpaid carers will be asked to promote the activities by joining in where appropriate as well as engaging in the goal setting process. Pictures of physical activity to be carried out may be provided to the participant to support them with the activity. Cueing cards will be embedded into the participant's daily life to encourage them to increase activity throughout the day. A structured proforma will be used during each visit to record the activities undertaken and recommendations of activities to be performed between visits. The proforma will include a review of whether the participant undertook the recommendations set out at the previous visit. If the participant has not adhered to the recommendations the reasons will be discussed with the participant and the goal setting will be reviewed.

The participant may also be referred to other local services for people who fall such as falls prevention classes. The GP will be sent a summary of the interventions carried out during the study after the final therapy visit as well as recommendations regarding ongoing service input where needed.

#### 8.2. Adverse events

#### 8.2.1. **Definitions**

Term	Definition	
Adverse Event (AE)	Any untoward medical occurrence in a participant to whom a medicinal product has been administered, including occurrences which are not necessarily caused by or related to that product.	
Serious Adverse Event (SAE)	
 
A serious adverse event is any untoward medical occurrence that:
 
results in death
 
is life-threatening
 
requires inpatient hospitalisation or prolongation of existing hospitalisation
 
results in persistent or significant disability/incapacity
 
consists of a congenital anomaly or birth defect
 
Other 'important medical events' may also be considered serious if they jeopardise the participant or require an intervention to prevent one of the above consequences.
 
NOTE: The term "life-threatening" in the definition of "serious" refers to an event in which the participant was at risk of death at the time of the event; it does not refer to an event which hypothetically might
 
	
Related and Unexpected SAE (RUSAE)	have caused death if it were more severe.  A related and unexpected SAE is an event which is related to the intervention; and 'unexpected' – that is, the type of event is not listed in the protocol as an expected occurrence.	

Table 4 Adverse Event definitions

### 8.3. Recording and reporting AEs, SAEs and RUSAEs

The Maintain study is a low risk, non-drug intervention trial. The interventions may be offered as part of a routine physiotherapy intervention. As dementia is progressive and associated with comorbidity, intercurrent illness will be common. We will only be recording and reporting safety data for patient participants.

#### Adverse events (AE)

Non-serious AEs will not be recorded or reported for the study. The components of the intervention are not novel and safety of the intervention is not an outcome measure.

### Serious adverse events (SAE)

All deaths (from any cause) and hospitalisations due to falls, fractures or musculoskeletal injury will be recorded. Other SAEs will not be recorded or reported. Only related SAEs will be subject to expedited reporting.

Causality of reportable SAEs will be assessed by the site PI (or authorised delegate). All SAEs which are possibly, probably or definitely related to the intervention will be categorised as 'related'. If the PI or delegate is unable to assign causality within 24 hours of the site becoming aware of the event, the SAE will be treated cautiously and subjected to expedited reporting.

### Related unexpected serious adverse events (RUSAE)

Death is an unexpected event. Deaths related to the intervention will be categorised as RUSAEs and subjected to expedited reporting.

### Not related or improbable

A clinical with temporal relationship to trial intervention which makes a causal relationship incompatible or for which other treatments, chemicals or disease provide a plausible explanation. This will be counted as "unrelated" for notification purposes.

#### Possible

A clinical event, with temporal relationship to trial intervention which makes a causal relationship a reasonable possibility, but which could also be explained by other interventions, chemicals or concurrent disease. This will be counted as "related" for notification purposes.

#### Probable

A clinical event, with temporal relationship to trial intervention which makes a causal relationship a reasonable possibility, and is unlikely to be due to other interventions, chemicals or concurrent disease. This will be counted as "related" for notification purposes.

#### Definite

A clinical event, with temporal relationship to trial intervention which makes a causal relationship a reasonable possibility, and which can definitely not be attributed to other causes. This will be counted as "related" for notification purposes.

#### Not assessable

There is insufficient or incomplete evidence to make a clinical judgement of the causal relationship.

#### Reporting procedure

- 1. If an adverse event is not classified as serious, no recording or reporting is required.
- 2. If an adverse event is classified as serious, but it is not a death or hospitalisation due to fall, fracture or musculoskeletal injury, no recording or reporting is required.
- 3. If the adverse event is serious, a death or hospitalisation due to fall, fracture or musculoskeletal injury, but not related to the intervention the Investigator must record the SAE on the CRF and no further reporting by site is required. The Exeter Clinical Trials Unit (ExeCTU) will report 3-monthly to the TMG, 6-monthly to the TSC and annually to the REC.
- 4. If the adverse event is serious, a death or hospitalisation due to fall, fracture or musculoskeletal injury, and related to the intervention the Investigator will report the SAE to ExeCTU within 24 hours of becoming aware of the event. ExeCTU will report to the sponsor within 24 hours of becoming aware of the event. If the event is death, the Sponsor or delegate will report to the TSC and REC within 7 days.

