# 3. Assessment and management of risk

### 3.1. Potential risks

As the patient population is made up of people living with dementia, they may lack the capacity to give informed consent and therefore be considered vulnerable.

Page 17 of 59

The intervention is comprised of physical activity which could result in injuries being sustained.

Patient participants will undertake the intervention at their home without medical assistance available if injuries occur, such as if the participant falls.

There is the potential impact of increased burden on both the patient participant and the carer participant when taking part in this study compared to usual care.

Visits from research support workers and therapists to the patient participants home introduce the risk of COVID-19 infection during these home visits.

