### 8.4. Responsibilities

At the 28 week follow-up visit the clinical researcher conducting the visit will ask if the patient participant has had a reportable SAE. Members of the research team at the site will also record all reportable SAE events into the EDC system before the 28 week follow-up time-point.

The principal investigator (PI) at site, or their authorised delegate, is responsible for assigning the severity and causality of an event, recording the SAEs as detailed in Section 8.3 of this protocol, and entering the data into the EDC system. The EDC will be set up with a role-restricted task to allow only the PI or delegate to sign off the reportable SAEs within the system.

The chief investigator (CI) or authorised delegate SAEs on a monthly basis and confirm their agreement or disagreement with the PIs judgement on causality. The CI will only upgrade, not downgrade, any decision made by the site PI. Disagreements will be discussed with the Sponsor, CI and PI and the Sponsor will be responsible for a final decision.

The TSC will review SAE data to identify if there are any patterns of events and to identify safety issues.

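### A related non-fatal SAE outside the listed admission types is never recorded as an SAE, although the protocol's RUSAE definition and reporting rule have no such limit

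*Protocol*

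**What the plan says.** The SAE paragraph of protocol section 8.3 sets the scope: "All deaths (from any cause) and hospitalisations due to falls, fractures or musculoskeletal injury will be recorded". The next sentence is "Other SAEs will not be recorded or reported", with no exception for related events. The sentence on causality begins "Causality of reportable SAEs will be assessed by the site PI (or authorised delegate", so relatedness is judged for events already classed as reportable. Of these, "All SAEs which are possibly, probably or definitely related to the intervention will be categorised as" related.

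The four-step reporting procedure follows the same order. Step 1 drops non-serious events. Step 2 drops a serious event if "it is not a death or hospitalisation due to fall, fracture or musculoskeletal injury, no recording or reporting is required". Relatedness first appears in steps 3 and 4. Unrelated events of the listed types go on the CRF. Related ones go to the CTU within 24 hours and then to the sponsor, and only deaths go on to the TSC and REC within 7 days.

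Table 4 in section 8.2.1 is wider: "A related and unexpected SAE is an event which is related to the intervention", and its type must not be among those the protocol lists as expected. The RUSAE paragraph in 8.3 then speaks only of deaths, while section 8.5 sends RUSAEs in general to the TSC and REC within 7 days. Section 8.4 states: "The TSC will review SAE data to identify if there are any patterns of events and to identify safety issues". Section 11 confirms that the TSC takes the role of data monitoring committee.

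**The concern.** A type filter is a reasonable way to keep background illness out of the safety data. It becomes a problem when it is applied before anyone asks whether the intervention caused the event. The protocol sets up a category for related events of unforeseen type, and then uses a procedure that stops most non-fatal members of that category from being identified. Examples are a cardiac admission, or a life-threatening or disabling event without an admission of a listed type, where the site would judge the event related.

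Two things are at stake. The committee asked to look for safety patterns would be looking at data from which these events are missing. The trial report would also give a count of related harms that is incomplete by construction, without the reader being able to tell.

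**Working it through.** There is no figure to reproduce. The check is to read the procedure as a decision table and compare it with the definitions.

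**Inputs.** Event type has three levels under 8.3: death; admission for a fall, fracture or musculoskeletal injury (listed admission); any other non-fatal SAE. Relatedness has two levels. That gives 3 x 2 = 6 cells.

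| Cell | Event | Related? | What 8.3 requires |
|---|---|---|---|
| 1 | Death | No | Recorded on the CRF (step 3) |
| 2 | Death | Yes | CTU within 24 hours, sponsor, then TSC and REC within 7 days (step 4) |
| 3 | Listed admission, non-fatal | No | Recorded on the CRF (step 3) |
| 4 | Listed admission, non-fatal | Yes | CTU within 24 hours, then sponsor (step 4) |
| 5 | Other non-fatal SAE | No | Nothing (step 2) |
| 6 | Other non-fatal SAE | Yes | Nothing (step 2) |

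**Comparison with Table 4.** A RUSAE must be related, so only cells 2, 4 and 6 can contain one.
- Cell 2 is handled as a RUSAE throughout.
- Cell 4 is recorded and expedited. Whether such an event is a RUSAE depends on a list of expected events, and the protocol text supplied contains no such list. If it is one, step 4 (onward reporting for deaths only) and section 8.5 (onward reporting for RUSAEs) disagree.
- Cell 6 meets the relatedness half of the definition and could meet the other half, yet it is dropped before either is asked.

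**Do the other safeguards reach cell 6?** Section 8.3 sends a reportable SAE for expedited reporting if causality cannot be assigned within 24 hours. Section 8.4 has the chief investigator review causality monthly, with upgrading only, and has the researcher ask about a reportable SAE at 28 weeks. All of these act on events that have already passed the filter.

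**Can analysis recover cell 6?** SAP section 5.6 reports harms that were collected, so it cannot.

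**The case against.** The narrow scope is deliberate. Section 8.3 describes a low-risk, non-drug trial in people for whom intercurrent illness will be common, and adds that the components are not novel and that safety is not an outcome. The injury risk named in section 3.1 is largely covered by cells 3 and 4. Other records may leave a trace: the HUQ shows service use, falls diaries give injury and fracture rates, session CRFs note why a session did not take place, and withdrawal forms may cite an adverse event. Urgent safety measures under section 8.7 apply to any immediate risk.

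Much of this stands, but it does not close cell 6. Common intercurrent illness is a reason to omit unrelated SAEs. The remarks on novelty and outcomes are made about non-serious events. None of the other records carries a causality assessment or triggers expedited reporting.

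Three stronger readings are tempting, and the documents do not support them.
- A reader might infer that no non-fatal SAE caused by the intervention is recorded. Step 4 shows otherwise for listed admissions.
- A reader might treat a COVID-19 admission as a clear lost RUSAE, since section 3.1 says home visits "introduce the risk of COVID-19 infection during these home visits". It would have to be both related and unexpected. Section 3.3 notes that participants are likely to have other exposure through home care or healthcare visits, section 8.3 counts an event as unrelated where another disease plausibly explains it, and a risk named in advance is arguably not unexpected.
- A reader might infer that an incomplete count would feed the progression decision. No stop/go criterion in section 4.4 concerns safety.

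**Conclusion.** The point holds for one of the six cells: a related non-fatal SAE that is not an admission for a fall, fracture or musculoskeletal injury. For that cell, step 2 and the sentence excluding other SAEs contradict Table 4 and section 8.5, and the TSC cannot see the event.

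The size in events is unknown, because the documents give no SAE rate. With 30 participants planned in the intervention arm, the number may be small or zero. The defect is that a zero in the report could not be read as evidence that no such event occurred.

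This should be corrected, but it does not undermine the pilot's feasibility results. The conclusion assumes that sites follow 8.3 as written and that the section is still current. SAP section 6 cites protocol version 5.0, whereas the protocol supplied is version 3.0, so a later change cannot be ruled out.

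**What to change.** First check section 8.3 in protocol version 5.0. If it is unchanged, reconcile Table 4, the SAE and RUSAE paragraphs and step 2 of 8.3, and sections 8.4 and 8.5, so that:
- an SAE outside the listed types goes unrecorded only if it is judged not related to the intervention;
- any SAE judged possibly, probably or definitely related is recorded and follows step 4, whatever its type;
- step 4, the RUSAE paragraph and section 8.5 agree on which events go to the TSC and REC within 7 days.

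Unrelated intercurrent illness stays unrecorded, which keeps the low-burden intent.

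The cost is more than one sentence. Sites must make a causality judgement on more SAEs, in a population where illness is common. The reportable-SAE wording in 8.3 and in the 28-week question in 8.4 needs matching edits, and so does the SAE form. There is also a reporting consequence: events recorded only because they are related can hardly arise in the control arm, so SAP section 5.6 should list them separately and not compare them between arms. The SAP was finalised during follow-up, so earlier events may already have gone unrecorded. In that case the harms table should state which types of SAE it covers.
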